#### 4.1.1.2 Secondary Definition of Progression Free Survival (Irrespective of Subsequent Therapy)

[figure not shown]
The secondary definition of PFS (ITT definition) is defined as the time between the date of randomization and the date of first documented tumor progression, based on BICR assessments (per RECIST v1.1 criteria), or death due to any cause, whichever occurs first.

Subjects who die without a reported progression will be considered to have progressed on the date of their death. The following censoring rules will be applied for the secondary definition of PFS:

- Subjects who did not progress or die will be censored on the date of their last evaluable tumor assessment.
- Subjects who did not have any on study tumor assessments and did not die will be censored on their date of randomization.

Censoring rules for the secondary definition of PFS (ITT definition) are presented as follows and in Figure 4.1.1.2-1 and in Table 4.1.1.2-1.

**Figure 4.1.1.2-1: PFS Secondary Definition**

**Table 4.1.1.2-1: Censoring Scheme for Secondary definition of PFS**

Situation	Date of Progression of Censoring	Outcome
No baseline tumor assessment	Date of randomization	Censored
No on-study tumor assessments and no death	Date of randomization	Censored
Documented progression per RECIST v1.1	Date of first documented progression per RECIST v1.1 criteria (excludes clinical progression)	Progressed
No progression and no death	Date of last evaluable tumor assessment	Censored
Death without progression per RECIST v1.1	Date of death	Progressed

Note: subjects with measurable disease per Investigator but no measurable disease per BICR will be included in the analysis.

#### **4.1.2 Overall Survival**

Overall survival is defined as the time from randomization to the date of death from any cause. For subjects that are alive, their survival time will be censored at the date of last contact (“last known alive date”). Overall survival will be censored for subjects at the date of randomization if they were randomized but had no follow-up.

The first survival follow-up will be conducted 3 months ( $\pm 14$  Days) after subject’s FU 2 visit, subsequent survival FU visits every 3 months ( $\pm 14$  days).

#### **4.1.3 Objective Response Rate**

Objective Response Rate (ORR) is defined as the number of randomized subjects who achieve a best response of complete response (CR) or partial response (PR) based on BICR assessments (using RECIST v1.1 criteria) divided by the number of randomized subjects. Best Overall Response (BOR) is defined as the best response, as determined by the BICR, recorded between the date of randomization and the date of objectively documented progression per RECIST v1.1 criteria or the date of subsequent therapy (including tumor-directed radiotherapy and tumor-directed surgery), whichever occurs first. For subjects without documented progression or subsequent therapy, all available response designations will contribute to the BOR determination. Confirmation of response is required at least 4 weeks after the initial response.

ORR will be summarized using a binomial response rate. The Clopper-Pearson method will be used to estimate the two-sided 95% confidence interval. BOR will be summarized by response category. Summary statistics of time to objective response will be provided for subjects who achieve a BOR of PR or CR, as assessed by the BICR.

Objective Response Rate as assessed by investigator will be summarized in the same manner as per BICR.

#### **4.1.4 Time to and Duration of Response**

Time to Response (TTR) is defined as the time from randomization to the date of the first confirmed documented response (CR or PR), as assessed by the BICR. TTR will be evaluated for responders (confirmed CR or PR) only.

Duration of Response (DOR) is defined as the time between the date of first documented response (CR or PR) to the date of the first documented tumor progression as determined by the BICR (per RECIST v1.1 criteria), or death due to any cause, whichever occurs first. Subjects who start subsequent therapy without a prior reported progression will be censored at the last evaluable tumor assessments prior to initiation of the subsequent anticancer therapy. Subjects who die without a reported prior progression will be considered to have progressed on the date of their death. Subjects who neither progress nor die, DOR will be censored on the date of their last evaluable tumor assessment. DOR will be evaluated for responders (CR or PR) only.

Duration of Response and time to response as assessed by investigator will be summarized in the same manner as per BICR.

[figure not shown]
#### **4.1.5 PFS2**

PFS on next-line therapy (PFS2) is defined as the time from randomization to objectively documented progression date after the next line of therapy, per investigator assessment, or to death from any cause, whichever occurs first. Subjects who were alive and without progression after the next line of therapy will be censored at last known alive date.

The following censoring rules will be applied for PFS2:

- Subjects who did not receive subsequent anti-cancer therapy (i.e. second-line therapy):
  - Subjects who died, the death date is the event date;
  - Else the subject's PFS2 is censored at his last known alive date.
- Subjects who received subsequent anti-cancer therapy (i.e. second-line therapy):
  - Subjects who had a disease progression after the start of subsequent anti-cancer therapy, this disease progression date is the event date;
  - Else if a subject died or discontinued subsequent anti-cancer therapy, the date of min (death, discontinuation of subsequent anti-cancer therapy) is the event date;
  - Else the subject's PFS2 is censored at his last known alive date.

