Laboratory Tests	X		For Follow-Up Visit 1, onsite/local including Hematology, Serum Chemistry, and Urinalysis as outlined in Table 9.4.4-1 . Repeat at Follow-Up Visit 2 if study treatment related toxicity persists.
Pregnancy Test (WOCBP only)	X		Pregnancy testing is only required at FU Visits 1 and 2 unless increased frequency and duration is required per local regulations.
Efficacy Assessments			
Body Imaging	X	X	Only for participants without BICR-confirmed progression on study therapy. Tumor assessments subsequent to the first assessment should occur every 8 weeks (± 1 week) up to Week 52 and then every 12 weeks (± 1 week) until disease progression is documented or study treatment is discontinued, whichever occurs later Contrast enhanced CT chest, CT (or MRI with and without contrast) abdomen, pelvis, and all known sites of disease. Use same imaging method as was used at screening/baseline. See Section 9.1 .

Table 2-3: Follow-Up Procedural Outline (CA224047)

Procedure	Follow-Up ^a Visits 1 and 2	Survival Follow-Up Visits ^b	Notes
Brain Imaging	X	X	Only for participants without BICR-confirmed progression on study therapy. Participants with a history of brain metastasis or symptoms should have surveillance MRIs per standard of care (approximately every 12 weeks) or sooner if clinically indicated. CT of the brain without and with contrast can be performed if MRI is contraindicated. See Section 9.1 . See Table 9.1.2-1 for instructions on performance of scans in participants with contrast allergies.
PFS2 Assessment	X	X	Following first progression, participants will continue to be followed during the safety and survival Follow-Up Visits. Time of second progression per investigator's assessment will be documented.
Pharmacokinetic (PK) Assessments			
PK and Immunogenicity blood sample	X		Refer to Table 9.5.1-1 for details regarding specific sample timing.
Outcomes Research Assessments			
EQ-5D-3L	X	X	For survival visits, questionnaire can be administered by phone. Pediatric participants (≥ 12 and < 18 years of age) should only complete the EQ-5D-3L and not the WPAI:GH or FACT-M assessments
FACT-M	X		
FACT-M melanoma subscale (MS)		X	For survival visits, MS questionnaire can be administered by phone.
WPAI:GH	X		
Health Care Utilization	X		Health care resource utilization data will be collected by study site staff using the CRF.

Table 2-3: Follow-Up Procedural Outline (CA224047)

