
 To characterize changes in cancer-related symptoms and quality of life for participants with unresectable or metastatic melanoma treated with BMS-986213 and those treated with nivolumab monotherapy 	
 Summary measures of FACT-M total and subscale scores (and changes) following treatment.

 To characterize participant perceptions of the bothersomeness of symptomatic AEs, based on FACIT GP5 item as found in the FACT-M. 	
 Summary changes and frequency of responses in FACIT GP5 item measuring bother due to side effects of treatment.

 To characterize changes in overall health status and health utility for participants with unresectable or metastatic melanoma treated 	
 Summary measures of EQ-5D-3L visual analog scale (VAS) and utility index scores.

Table 4-1: Objectives and Endpoints

Objectives	Endpoints
with BMS-986213 and those treated with nivolumab monotherapy.	

 To characterize changes in work productivity and activity impairment for participants with unresectable or metastatic melanoma treated with BMS-986213 and those treated with nivolumab monotherapy 	
 Summary measures of Work Productivity and Activity Impairment General Health (WPAI:GH) work productivity loss, activity impairment, presenteeism, and absenteeism scores.

 To evaluate PFS, PFS after next line of treatment (PFS2), ORR, and DOR of BMS-986213 to nivolumab monotherapy in participants with previously untreated, unresectable, or metastatic melanoma 	
 PFS and PFS2 time as assessed by investigator using RECIST v1.1. ORR as assessed by investigator. DOR.

 To evaluate treatment-free interval (TFI) defined as time from last dose of study treatment to the start of subsequent systemic therapy or the last known date alive (for those who never received subsequent cancer therapy) 	
 TFI
Phase 2 Primary Objective	

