To evaluate PFS, PFS 2, ORR, and DOR of BMS-986213 to nivolumab monotherapy in participants with previously untreated, unresectable, or metastatic melanoma	
PFS and PFS 2 time as assessed by investigator using RECIST v1.1.
 
ORR as assessed by investigator.
 
DOR.

To evaluate treatment-free interval (TFI) defined as time from last dose of study treatment to the start of subsequent systemic therapy or the last known date alive (for those who never received subsequent cancer therapy)	TFI
Phase 3 Safety Objective:	
To assess the overall safety and tolerability of BMS-986213 and of nivolumab monotherapy.	Rate of AEs, SAEs, AEs leading to discontinuation of treatment, deaths, and laboratory abnormalities.

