- 1) PFS using stratification factors as obtained from the baseline CRF pages (instead of IRT). The hazard ratio associated with treatment will be presented along with the associated two-sided 95% CIs. This analysis will be performed only if at least one stratification variable/factor at randomization (as per IRT) and baseline are not concordant for at least 10% of the randomized subjects.
- 2) PFS using the investigator's assessment. The hazard ratio associated with treatment and median PFS will be presented along with the associated two-sided 95% CIs.
- 3) PFS using an un-stratified log rank test. The hazard ratio associated with treatment will be presented along with the associated two-sided 95% CIs.
- 4) PFS using an unstratified Cox proportional hazards model, adjusted, using as covariates only the four stratification factors used in randomization. The hazard ratio associated with treatment will be presented along with the associated two-sided 95% CIs.
- 5) PFS for subjects with no relevant protocol deviations. This analysis will be conducted only if there are more than 10% subjects with relevant protocol deviations. The hazard ratio associated with treatment will be presented along with the associated two-sided 95% CIs.
- 6) During the course of this study a global pandemic occurred known as COVID-19. A sensitivity analysis will be performed if 10% of all PFS events were due to COVID-19. Subjects with a COVID-19 PFS event (i.e., death) will be censored on the previous evaluable image. The hazard ratio associated with treatment will be presented along with the associated two-sided 95% CIs.

A by-subject listing will be presented including treatment group, PFS duration under the primary definition, PFS duration on the ITT definition, whether the subject was censored under the primary definition, and if censored, the reason, and whether the subject was censored under the ITT definition, and if censored, the reason.

PFS2 will be analyzed similarly to PFS:

- Median values based on KM method, along with two-sided 95% CI using Brookmeyer and Crowley method will be calculated. The estimate of standard error will be calculated using the Greenwood formula;
- PFS2 will be graphically displayed along with the median and 95% CI. By-subject listing of PFS and PFS 2 will be provided.

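### SAP 4.1.5 gives PFS2 two different event rules (stopping next-line therapy counts in one but not the other), and SAP 4.1.6 does the same for treatment-free survival (TFS)

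*SAP*

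**What the plan says.** **PFS2.** The opening sentence of SAP 4.1.5 measures PFS2 from randomization and names two events: progression after the next line of therapy, as assessed by the investigator, and death from any cause. The next sentence covers everyone else: "Subjects who were alive and without progression after the next line of therapy will be censored at last known alive date".

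A list follows, introduced by "The following censoring rules will be applied for PFS2". For participants who received subsequent therapy it has three ordered branches:

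- A second progression, once next-line therapy has begun, is the event and supplies its date.
- Where no such progression is recorded, the second branch reads: "Else if a subject died or discontinued subsequent anti-cancer therapy, the date of min (death, discontinuation of subsequent anti-cancer therapy) is the event date"
- Everyone remaining is censored when last known to be alive.

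Elsewhere the documents say little about PFS2 events. Protocol Table 4-1 has "PFS and PFS2 time as assessed by investigator using RECIST v1.1" and SAP Table 3-1 has "PFS and PFS 2 time as assessed by investigator using RECIST v1.1". The follow-up schedule in Protocol Table 2-3 says "Time of second progression per investigator's assessment will be documented". For the analysis, SAP 7.5.2 says "Median values based on KM method, along with two-sided 95% CI using Brookmeyer and Crowley method will be calculated" and adds a plot and a by-subject listing.

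**TFS.** SAP 4.1.6 has two consecutive sentences about TFS. One makes the event subsequent therapy or death, whichever is earlier. The other sets the TFS time equal to TFI and makes subsequent therapy the only event. SAP 7.5.10 plans medians, rates from 1 to 60 months and Kaplan-Meier plots for both TFI and TFS.

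**The concern.** An endpoint needs one event rule. In 4.1.5 the definition and the rules to be applied do not match, so two programmers working from the same section could produce different PFS2 medians, curves and listings. A result produced under the branch rules would also not be the endpoint that the definition describes. The same holds for TFS: deaths without subsequent therapy are events under one sentence and not under the other.

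The timing matters too. SAP 5.2.1 records that the primary PFS analysis was tested on 09MAR2021 and led to subject-level unblinding. A choice between two written rules should now be stated and dated, not settled silently in programming.

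**Working it through.** No arithmetic applies and the plan gives no figure to reproduce. The check sets the rules side by side and applies each to the possible participant histories.

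**Assumption.** Progression after the next line is read as progression after that line has started, and recorded progression is taken to be objectively documented. The definition and the first branch are worded slightly differently on this, so the agreement shown below depends on that reading.

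**PFS2 histories.** Without next-line therapy there are 2 patterns (died or not). With it there are 2 × 2 × 2 = 8 (second progression, discontinuation, death, each yes or no). That makes 10.

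- No next-line therapy (2 patterns): death is the event, otherwise censored. The texts agree.
- Next-line therapy with second progression (4 patterns): the event is at progression under both texts. They agree, even if therapy stopped before progression, because the progression branch comes first.
- Next-line therapy, no progression, not stopped (2 patterns): death is the event, otherwise censored. They agree.
- Next-line therapy, no progression, stopped (2 patterns): they disagree.

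So the texts agree in 8 patterns and differ in 2. With illustrative months:

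| Participant | Definition | Branch rule |
|---|---|---|
| Stops next-line therapy at month 14, alive without progression at month 30 | Censored at 30 | Event at 14 |
| Stops at month 14, dies at month 20 without progression | Event at 20 | Event at 14 |
| Stops at month 14, progresses at month 18 | Event at 18 | Event at 18 |

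The first row changes event status. The second changes the event date only.

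**TFS histories.** Crossing subsequent therapy (yes or no) with death (yes or no) gives 4 patterns. The two sentences differ in one, death without subsequent therapy. A participant who dies 5 months after the end of study therapy, with no subsequent therapy, has an event at 5 months under one sentence and none under the other.

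**Does other text settle it?** The two endpoint tables name the assessor and the criteria for PFS2 but list no events. Table 2-3 is a collection instruction. SAP 7.5.2 gives estimation methods only. Figure 4.1.5-1, which illustrates the PFS2 definition, is not shown in the copy reviewed. It may favour one rule, but the two written texts would still differ.

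**The case against.** The best defence is that the branch rules are ordered, cover every case and are the ones the SAP says will be applied, so a programmer can implement them. On that view the opening paragraph is only an incomplete summary and the remedy is editorial. This is fair as to weight. It does not remove the conflict, because the sentence on censoring in the definition assigns a different outcome to the same participant.

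On TFS, the second sentence is probably a slip for TFI: it refers to the TFI time, and TFI has no event rule otherwise. That is accepted as the likely reading, but it remains an inference and the text needs correcting. A reader might conclude that TFS will be analysed as a copy of TFI; the documents do not show that this is intended.

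Other stronger readings are tempting but unsupported:

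- **The objectives tables rule out discontinuation as an event.** They do not. They list no PFS2 events, not even death, so their silence proves nothing.
- **The branch rule is the wrong one, or favours one arm.** Nothing in the documents establishes which rule is better, or how stopping next-line therapy is distributed between arms.
- **The PFS2 rule was changed after unblinding.** The SAP document history has no entry on the PFS2 event rule and records no such change.
- **Readers of the report will not be told that stopping counts.** Section 4.1.5 states it, and the table and listing mock-ups are in a Data Presentation Plan that was not available.

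**Conclusion.** The concern holds as an inconsistency of wording that affects reported results. Section 4.1.5 gives two event rules for participants who stopped next-line therapy with no recorded second progression, and section 4.1.6 gives two for participants who died without subsequent therapy. No text available for review resolves either conflict.

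The size cannot be determined. The documents do not say how many participants started or stopped next-line therapy, or how many died without it. The direction of any effect on the treatment comparison is equally unknown.

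Importance is low. PFS2 and TFI are exploratory and TFS is not a listed objective. SAP 5.2.1 limits formal testing to PFS, OS and ORR, so those endpoints and the alpha are unaffected. The conflict itself is certain from the text. That the other PFS2 patterns agree rests on the reading of progression stated in the check.

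**What to change.** In SAP 4.1.5, make the definition, the branch rules and Figure 4.1.5-1 state one event list. Report PFS2 in two versions, one counting progression or death and one also counting discontinuation of next-line therapy. Label one as main and the other as sensitivity. The documents do not decide which should be main, so the sponsor should choose and record the choice, with its timing relative to unblinding, in the document history.

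In SAP 4.1.6, define the TFS event as subsequent therapy or death and reword the second sentence so that it refers to TFI.

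The cost is a few sentences, a document-history entry and one extra exploratory analysis. The discontinuation version needs stop dates for next-line therapy. The branch rule already presupposes them, but the documents do not confirm that they are collected, so this should be checked. The downsides are a wording change after unblinding and two PFS2 results to explain in the report.

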**Figure 4.1.5-1: PFS2 Definition**

#### 4.1.6 TFI

Treatment-Free Interval (TFI) and Treatment-Free Survival (TFS) are defined only in randomized participants who are off study treatment and continued to be followed in study prior to initiation of subsequent systemic therapy. TFI is defined as time from end of study therapy until last known alive date in those who never received subsequent systemic therapy, and defined as time from end of study therapy until subsequent systemic therapy in those who received subsequent systemic therapy. For TFS, event is defined as receiving subsequent therapy or death, whichever comes first. For TFS, time is TFI and event is receiving subsequent therapy.

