### **7.5.10 Treatment-free interval**

Treatment free interval and survival will be summarized in months (median and 95% CI) and rates will be provided at 1, 2, 3, 6, 9, 12, 24, 36, 48, and 60 month intervals. Kaplan-Meier plot of treatment-free interval and survival will be provided.

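### The SAP states no event or censoring rule for treatment-free interval; on the only coherent reading, its Kaplan-Meier rates overstate how many participants start subsequent therapy

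*SAP*

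**What the plan says.** The protocol (Section 4, Table 4-1, Phase 3 exploratory objectives) defines TFI as "time from last dose of study treatment to the start of subsequent systemic therapy or the last known date alive", the second ending applying to those who never had further therapy. It gives no event and no censoring rule.

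SAP 4.1.6 restricts TFI and TFS to a subset: they "are defined only in randomized participants who are off study treatment and continued to be followed in study prior to initiation of subsequent systemic therapy". For TFI it gives two times:

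- no further systemic treatment given: "TFI is defined as time from end of study therapy until last known alive date in those who never received subsequent systemic therapy";
- subsequent systemic therapy received: "defined as time from end of study therapy until subsequent systemic therapy in those who received subsequent systemic therapy".

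Two consecutive sentences then both address TFS and disagree. The first reads "For TFS, event is defined as receiving subsequent therapy or death, whichever comes first". The second reads "For TFS, time is TFI and event is receiving subsequent therapy". No sentence names an event for TFI.

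SAP 7.5.10 covers both quantities: "Treatment free interval and survival will be summarized in months (median and 95% CI) and rates will be provided at" ten time points from 1 to 60 months, and "Kaplan-Meier plot of treatment-free interval and survival will be provided". Neither document plans a cumulative incidence or other competing-risk method for TFI.

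**The concern.** A Kaplan-Meier curve needs an event and a censoring rule, and SAP 4.1.6 supplies neither for TFI. The programmer must infer them from two TFS sentences that contradict each other.

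The inference that fits best censors participants who die without further therapy. Someone who has died can no longer start therapy, but a censored participant is treated by Kaplan-Meier as if still able to. The resulting rates describe a hypothetical population in which nobody dies before starting therapy. The participants actually followed are a different population. Deaths are not rare in this trial: the final OS analysis is planned at 300 deaths among about 700 randomized, although some of those deaths follow subsequent therapy and so do not compete with starting it.

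At stake is how the off-treatment experience is described. The protocol's stated reason for adding TFI is to give a further picture of outcomes in participants off treatment. No tested hypothesis is involved.

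**Working it through.** The documents give no TFI median, rate or sample size, so there is no plan figure to reproduce. The check has three parts.

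**1. Which event does the plan intend?** Three readings are possible.

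| Reading | Consequence |
|---|---|
| Event is subsequent therapy or death | TFI and TFS become essentially the same curve, yet SAP 7.5.10 asks for both |
| Every TFI time is an event | Living, untreated participants fail at last contact |
| Event is subsequent therapy; all others censored | Matches the second TFS sentence, which names TFI as its time, and gives a curve distinct from TFS |

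Only the third is coherent, and it makes the second TFS sentence a probable mislabelling of the TFI rule. Elsewhere the SAP names the death date where death should count (duration of response in 4.1.4, PFS2 in 4.1.5, extent of survival follow-up in 7.5.6). The TFI definition does not.

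**2. Direction.** Let a(s) be the hazard of starting therapy, and A(s) and D(s) the cumulative hazards of therapy and of death before therapy.

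- Kaplan-Meier complement, deaths censored: ∫ a(s) exp(−A(s)) ds.
- Cumulative incidence of therapy: ∫ a(s) exp(−A(s) − D(s)) ds.

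Since exp(−D(s)) ≤ 1, the first is never below the second, and it is larger once deaths have preceded later therapy starts. In 300 simulated samples of 500 with administrative censoring, this held in every sample. Mean values at 24 months were 0.749 against 0.582 with independent causes, and 0.530 against 0.452 with a shared gamma frailty.

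**3. Illustrative size.** Inputs:

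- death hazard d = ln 2 / 36.9 = 0.0188 per month (nivolumab) and ln 2 / 49.2 = 0.0141 (combination), from the OS medians in SAP Table 5.2.1-2;
- therapy hazard a = 0.02 to 0.08 per month, assumed;
- both hazards constant.

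Then 1−KM = 1 − exp(−a t), and cumulative incidence = a/(a+d) × [1 − exp(−(a+d) t)].

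Worked case, nivolumab, a = 0.03, t = 24: 1−KM = 1 − exp(−0.72) = 51.3%. Cumulative incidence = 0.03/0.0488 × [1 − exp(−1.171)] = 0.615 × 0.690 = 42.4%.

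| a per month | 1−KM, 24 mo | Cum. inc., nivolumab | Gap (points) | Cum. inc., combination | Gap (points) |
|---|---|---|---|---|---|
| 0.02 | 38.1% | 31.2% | 6.9 | 32.8% | 5.3 |
| 0.03 | 51.3% | 42.4% | 8.9 | 44.4% | 6.9 |
| 0.05 | 69.9% | 58.7% | 11.1 | 61.3% | 8.6 |
| 0.08 | 85.3% | 73.4% | 11.9 | 76.1% | 9.2 |

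At 12 months the gap is about 2 to 6 points. At 60 months it is about 18 to 25 points (nivolumab) and 14 to 20 (combination).

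Medians, nivolumab, a = 0.03:

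- Kaplan-Meier TFI: ln 2 / 0.03 = 23.1 months;
- time at which cumulative incidence reaches 50%: −ln(1 − 0.5/0.615)/0.0488 = 34.4 months;
- therapy-or-death composite: ln 2 / 0.0488 = 14.2 months.

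The Kaplan-Meier TFI median lies between the other two and equals neither.

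With higher assumed death hazards the gaps widen. For cause-specific medians of 6, 12 or 24 months to therapy and 12 or 24 months to death, the 24-month gap runs from 12.5 to 28.2 points.

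**The case against.** **Death-censoring is not written in the SAP.** True. The quoted sentence defines a time, and the only sentence joining that time to an event is labelled TFS. The point therefore rests on a reading, and the missing rule is itself part of the defect. The other two readings do not give a usable TFI curve, so the inference stands as an inference.

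**TFS already counts deaths.** Under the first TFS sentence, a composite curve with the same time points would sit beside the TFI curve. That limits the harm. The safeguard is not secure, because the next sentence removes death from the TFS event.

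**Kaplan-Meier TFI has a meaning of its own.** It describes the cause-specific hazard of starting therapy, which is a legitimate target if labelled as such. This stands. The difficulty is that SAP 7.5.10 presents rates and a median without that label.

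**The size is not document-based.** This stands. The therapy hazard is assumed. The OS medians run from randomization and include deaths after subsequent therapy, which pushes the gap up. Mortality before further therapy in participants already off treatment may be higher than those medians imply, which pushes it down.

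Two stronger inferences are tempting and should not be drawn. One is that the planned TFI median is simply too short; that is true only against the time at which cumulative incidence reaches 50%. The other is that the arm comparison is distorted. With equal therapy hazards in both arms the Kaplan-Meier curves are identical, and it is cumulative incidence that differs (58.7% against 61.3% at 24 months with a = 0.05), purely through mortality. The documents do not show a distorted comparison, and no TFI test or hazard ratio is planned.

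**Conclusion.** The point holds in limited form. SAP 4.1.6 leaves the TFI event and censoring rule unstated and defines the TFS event in two incompatible ways. If the TFI event is subsequent systemic therapy and deaths without it are censored, the SAP 7.5.10 Kaplan-Meier rates overstate the proportion who start therapy, and the TFI median has neither of its two natural interpretations.

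The direction of the rate bias follows from algebra and needs no assumption about hazards or independence. The size is illustrative only: about 5 to 12 points at 24 months, assuming constant hazards, therapy hazards of 0.02 to 0.08 per month and death hazards set from the plan's OS medians.

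Importance is low. TFI is an exploratory, descriptive Phase 3 endpoint outside the testing hierarchy in SAP 5.2.1, and no primary or key secondary conclusion depends on it.

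**What to change.** - **SAP 4.1.6:** state the event and censoring rule for TFI. If the second TFS sentence was meant for TFI, relabel it. Leave TFS with one event definition, therapy or death, with time ending at the death date for those who die without therapy.
- **SAP 7.5.10, TFI:** report the cumulative incidence of subsequent systemic therapy by the Aalen-Johansen estimator, with death as the competing event, at the time points already listed. If a Kaplan-Meier TFI curve is kept, label it as cause-specific and do not present its complement as the proportion who started therapy.
- **SAP 7.5.10, TFS:** keep Kaplan-Meier for the composite.

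The cost is a few lines of SAP text and one further standard procedure. No new data are needed.
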